9.3.5 Final Visit or Early Termination

For all **randomized** Subjects who complete the trial as scheduled, the assessments described for V6 must be performed at trial completion. If premature discontinuation after V3 occurs, the following will apply:

- All assessments described for visit V6 must be performed with exception for the bronchoscopy with bronchial biopsy and their related procedures (the bronchoscopy with bronchial biopsy

and their related procedures can only be done upon the Subject's agreement) and the CRF Disposition Page must be completed.

The Disposition Page of the CRF must be completed for all randomized and non-randomized Subjects, terminating the trial (either as scheduled or prematurely). For Subjects terminating prematurely the reason for the premature termination has to be documented. The confirmation of the clinical Investigator, that the Subject has been treated under his/her supervision and data are correctly recorded will be documented in this Disposition CRF Page.

After terminating the trial (after VE) Subjects will be treated according to their medical needs.

9.3.6 Follow-up / Visit V7 (≤ 2 weeks after visit V6)

For all randomized Subjects who completed the trial as scheduled and the final bronchial biopsy was performed at V6, a follow-up visit (V7) will be performed within two weeks after V6 to receive information about the Subject's well being after the bronchoscopy.

The following assessments or procedures will be performed:

- Concomitant medications (see Sections 7.6, 7.7, 9.1.7)
- Physical examination (see Section 9.1.3)
- Vital signs (e.g. heart rate, blood pressure) and body measurements (body weight and height) (see Sections 9.1.4, 9.1.5)
- Adverse event assessment

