2.0 STUDY SUMMARY

Name of Sponsor(s): Takeda Development Centre Europe Ltd.		Compound: Roflumilast	
Title of Protocol: A 16-week, randomized, placebo-controlled, double blind, and parallel group trial to assess the anti-inflammatory effects of Roflumilast in chronic obstructive pulmonary disease The ROBERT study		IND No.: Not Applicable	EudraCT No.: 2011-000582-13
Study Number: RO-2455-402-RD		Phase: III Clinical Exploratory	
Study Design: This is a phase III, randomized, placebo-controlled, double blind, and parallel group trial to assess the anti-inflammatory effects of Roflumilast in chronic obstructive pulmonary disease. The duration is 24 weeks maximum, and consists of the following periods: 
 • Single-blind placebo run-in period (6 weeks) with visits scheduled at weeks: -6 (V0), -2 (V1) and 0 (V2, randomization visit). • Double-blind treatment period (16 weeks) with visits scheduled at 6, 14, and 16 weeks of treatment (V4-V6). An additional visit V3 will have to be performed within two weeks after bronchoscopy/bronchial biopsy purely as a safety visit. The exact timing of this safety visit will be determined by the Investigator. • Safety follow-up. All adverse events (AEs) will be followed up to 30 days after the double-blind treatment period has been completed. An additional safety visit V7 will be scheduled within 2 weeks after the second bronchoscopy. The exact timing of the safety visit will be determined by the Investigator. 			
Primary Objectives: 
 • To investigate the effect of Roflumilast 500 µg tablets once daily versus placebo on inflammatory cells (CD8+) in bronchial biopsy tissue specimens. 			
Secondary Objectives: 
 • To investigate inflammatory cells and parameters in bronchial biopsy tissue, sputum and blood serum. • Safety status will be assessed by vital signs, physical examination (including electrocardiogram [ECG]), clinical laboratory tests, and monitoring of adverse events. 			
Subject Population: Patients with COPD (GOLD stage II-III, in Germany stage II only)			
Number of Subjects: A total of 150 Subjects is to be randomized (1:1) into two treatment arms (Roflumilast 500 µg or placebo).		Number of Sites: Estimated total: Approximately 25 sites in Europe.	

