Bronchoscopy is a relatively safe procedure. Serious risks from bronchoscopy, such as an air leak or serious bleeding are reported in less than 5 % of procedures. Other risks associated with the procedure are as follows: bleeding, discomfort and coughing, reduced oxygen, lung leak or collapse (pneumothorax) [12]. Bronchoscopy has an invaluable place in airway research. Given that the safety of the volunteer Subject is of paramount importance, the conduct of the clinical trials should be based on well established methods [13]. The individual risk to the Subjects from the bronchoscopy/bronchial biopsy procedure is as minimized based on several principles implemented within the protocol. The bronchoscopy and bronchial biopsy will only be conducted at experienced investigational sites which have shown in previous clinical trials to be capable of performing bronchoscopies in a standardized and safe manner. The same predefined, standardized procedures will be followed, the sites will be individually trained on the trial related procedures, and the quality of the biopsied material will be validated for each site. Dedicated safety follow-up visits have been implemented in the trial schedule subsequent to each visit with a bronchoscopy assessment. In addition, the sputum collection sampling has been separated from the bronchoscopy visits in order to not perform too many interventions on the same day.

A treatment regimen with a once daily dose of Roflumilast 500 µg was effective and safe in several clinical trials assessing COPD patients of GOLD stages II-IV. DAXAS[®] (Roflumilast 500 µg) was approved in the European Union by the European Commission on 5 July 2010 for the maintenance treatment of severe COPD (FEV₁ post-bronchodilator less than 50% predicted) associated with chronic bronchitis in adult patients with a history of frequent exacerbations as add on to bronchodilator treatment. In the U.S.A., Roflumilast 500 µg (DALIRESP[®]) was approved by FDA on 28 February 2011 as a treatment to reduce the risk of COPD exacerbations in Subjects with severe COPD associated with chronic bronchitis and a history of exacerbations.

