9.1.3 Physical Examination Procedure

A routine physical examination will be done at visits V0, V2, V6, and for Subjects who underwent the second biopsy as planned, at visit V7. Physical examinations will cover eyes, ears, nose, throat, lungs/thorax, heart/cardiovascular system, abdomen, skin and mucosae, nervous system, lymph nodes, musculo-skeletal system, and, if applicable, others. Any new clinically relevant finding compared to visit V0 must be documented as AE in the CRF.

If any clinically relevant finding will be observed at visit V0, these must be documented in the Medical History (MH) section of the CRF.

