9.1.15 Bronchoscopy

Bronchoscopy will be performed at visit V2 (randomization visit) and at visit V6 (subsequent to 16 weeks of treatment) in line with the American Thoracic Society guidelines and Endobronchial Biopsy Workshop [13, 18], a slightly modified, protocol of O'Shaughnessy et al. [1997] [19], and according to clinical standards of care at the site.

Endobronchial biopsies will be taken from each the lobar and sub segmental carinae. At each bronchoscopy session, in order to take into account within-Subject variability, 2-3 biopsies will be taken from the lobar bronchus and 2-3 from the sub-segmental airways. Additionally the left and right lobes will be alternated per Subject, but all biopsies will be harvested from one lung at a given session. Cup forceps will be provided by the Sponsor for the sole use in the course of this trial to maintain the specimen quality. However, other suitable forceps may also be used.

Although bronchoscopy is considered to be safe procedures in patients with COPD [20], Subjects will be closely monitored after bronchoscopy for at least 2 h. Subjects will only be discharged when the effects of sedation and local anaesthesia disappear and no hypoxemia, while breathing room air will be observed. All Subjects will be given a 24 h emergency contact number.

Additionally a safety visit will be performed within two weeks, during which the respective Investigator will see the Subjects, after each bronchoscopy session.

Further details are described in the Bronchoscopy Manual ([Appendix F](#)).

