Appendix A Schedule of Study Procedures

Activities and assessments	Run-in period			Double-blind treatment period				FU safety visit ^{a)}
			R				VE	
Visit	V0	V1	V2	V3	V4	V5	V6	V7
Weeks	-6	-2	0	≤2	6	14	16	≤18
Visit Window (days) ^{b)}		-2 / +3	-3 / +5		-3 / +5	-3 / +5	-7 / +7	
Subject Information and Informed Consent	X							
Demographic data	X							
Medical History and concomitant diseases	X							
COPD history	X							
Inclusion/Exclusion criteria	X							
Withdrawal of disallowed medications	X							
Previous and concomitant medications	X	X	X	X	X	X	X	X
Substance use (smoking status)	X	X	X		X	X	X	
Physical examination	X		X				X	X
Vital signs and body measurements (including body weight and body height) ^{c)}	X	X	X	X	X	X	X	X
Subject fasting, avoidance of strenuous exercise and smoking	X	X ^{d)}	X	X*	X*	X*	X	X*
Standard laboratory (including blood pregnancy test) ^{e)}	X	X ^{d)}					X	
Urine analysis	X							
Urine pregnancy test ^{e)}		X	X		X	X		
Clotting time and platelet count	X	X				X		
Blood sampling for assessment of inflammatory biomarkers and metabolites in blood serum		X			X	X		
Sputum induction and sputum sample processing		X			X	X		
Bronchoscopy/bronchial biopsy			X				X	
Pulse oximetry measurement			X				X	
Chest X-ray or CT scan ^{f)} GERMANY ONLY: Check of historical chest X-ray or CT scan ^{f)}	X							
ECG (12-lead) at rest ^{g)}	X							
Pulmonary function test	X		X				X	

Activities and assessments	Run-in period			Double-blind treatment period				FU safety visit ^{a)}
Randomization criteria check			X					
Randomization			X					
ID card dispensed	X							
Adverse event assessment (see Section 10.0)	X	X	X	X	X	X	X	X
Dispense trial treatment	X		X		X			
Trial treatment returned			X		X		X	
Tablet compliance check			X ^{b)}		X		X	
Termination of double-blind treatment phase of the trial							X	

Notes:

- V3 and V7, which are safety visits only, are to be conducted within two weeks after bronchoscopy. The exact timing remains at the discretion of the Investigator.
- Assessments described under V6 (VE) are mandatory for randomized Subjects upon trial completion either prematurely or as scheduled.
- In selected Subjects three protected brush specimen in a middle lobe bronchus will be collected at visits V2 and V6. This is described in a separate sub-trial protocol. With regard to Subject consent and information this sub-trial is independent from the RO-2455-402-RD trial protocol (see Section 9.1.15.3).

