Bronchoscopies will be performed at each site. If possible a bronchoscope with a large diameter is preferred.

Disposable biopsy forceps provided by Takeda can be used for each Subject.

During the biopsy procedure a Biopsy Collection Worksheet (see [Appendix G](#)) must be completed. The top copy of this completed worksheet must be sent with the samples via courier to

laboratory for analyses. The second copy should be retained at the investigational site and filed in the Case Report Form (CRF) of the Subject.

Procedure of bronchoscopy

Sites should follow their standard hospital procedures for the medical and nursing care of the Subjects during and following the bronchoscopy.

All patients will be given a 24 h emergency contact number and will be followed up by phone within 24-48 h by the Investigator. Additionally a safety visit (visit V3 and V7) will be performed within 2 weeks, during which the respective Investigator will see the Subjects after each bronchoscopy session.

All medication administered at the time of bronchoscopy must be recorded in the Case Report Form (CRF) on the concomitant medication form.

Any adverse events (AEs) relating to the bronchoscopy must also be documented in the CRF on the Adverse Event form. Any serious adverse event (SAE) that occurs during or following the bronchoscopy, e.g. severe bleeding, pneumothorax or necessity for an overnight stay in hospital must be reported within 24 hours of occurrence by completing a SAE form and send to Takeda (for details, see Section 10.2.2 in the trial protocol).

Procedure of biopsy

Six endobronchial biopsies of adequate size will be taken from two airway generations (level). Biopsies from the lobar and sub segmental carinae areal will be collected.

On each biopsy occasion the biopsy size and overall quality (free of blood) should be macroscopically inspected by the bronchoscopist/assistant.

As two airway levels (i.e. lobar carinae and subsegmental carinae) are biopsied, the biopsies from these two sites should be separately recorded i.e. those from the lobar carinae labelled with the prefix A and those from the subsegmental carinae region labelled with the prefix B. For these two levels there should be 2-3 good quality biopsies for each site. The biopsies should be immediately placed in fixative. To avoid mixing of samples a plastic specimen should be used for each tissue sample.

The following information must be written on this plastic specimen using a histology pen;

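### Section 9.3.6 limits the post-bronchoscopy safety visit V7 to scheduled completers, although the second bronchoscopy may also be done at early termination and other sections require a visit after it

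*Protocol*

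**What the plan says.** Three parts of the protocol bear on who has V7.

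- **When the second bronchoscopy can happen.** It is planned for V6. Under section 9.3.5, a subject who discontinues prematurely after V3 has all V6 assessments except the bronchoscopy with biopsy, which "and their related procedures can only be done upon the" subject's agreement. It is therefore optional at early termination, but allowed.
- **Where V7 is restricted.** Section 9.3.6, the section that defines V7, opens with "For all randomized Subjects who completed the trial as scheduled and the final bronchial biopsy was performed at V6". Section 9.1.3 schedules the physical examination at V0, V2 and V6 and, "for Subjects who underwent the second biopsy as planned, at visit V7".
- **Where the safety visit follows the bronchoscopy without a completion condition.** Sections 2.0 and 6.1: "An additional safety visit V7 will be scheduled within 2 weeks after the second bronchoscopy". Section 6.2: "Dedicated safety follow-up visits have been implemented in the trial schedule subsequent to each visit with a bronchoscopy assessment". Section 9.1.15: "Additionally a safety visit will be performed within two weeks, during which the respective Investigator will see the Subjects, after each bronchoscopy session". Appendix A, notes: "V3 and V7, which are safety visits only, are to be conducted within two weeks after bronchoscopy". Appendix F: "Additionally a safety visit (visit V3 and V7) will be performed within 2 weeks", after each session.

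**The concern.** The sections do not agree on whether a subject who leaves early but accepts the second bronchoscopy is seen afterwards. A site working from 9.3.6 would close the subject out without the visit and its physical examination. A site working from 9.1.15 or Appendix F would bring the subject back.

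What is at stake is safety follow-up after an invasive research procedure. Section 6.2 presents the dedicated visit after every bronchoscopy as one of the ways individual risk is minimized, and under 9.3.6 that assurance fails for this group. Section 7.8 lists adverse events and deteriorating lung function among the reasons for stopping, so early leavers may include subjects for whom such a check is useful.

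**Working it through.** No arithmetic applies. The check takes one case through each section.

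**Case:** a randomized subject discontinues after V3, has not withdrawn consent, and agrees to the second bronchoscopy at the early-termination visit, as 9.3.5 permits.

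| Section | What triggers V7 | Is this subject covered? |
|---|---|---|
| 9.3.6 | Completed as scheduled **and** final biopsy at V6 | No |
| 9.1.3 (examination only) | Second biopsy as planned | No, on the ordinary reading |
| 2.0 and 6.1 | Second bronchoscopy | Yes |
| 6.2 | Each visit with a bronchoscopy | Yes |
| 9.1.15 | Each bronchoscopy session | Yes |
| Appendix A, note | Bronchoscopy, within two weeks | Yes |
| Appendix F | Each bronchoscopy session, V7 named | Yes |

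**Comparison cases.** A subject who completes and is bronchoscoped at V6 has V7 under every row. A subject who leaves early and declines the bronchoscopy has no V7 under any row. The sections diverge only for the early leaver who is bronchoscoped.

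**Can the completer condition be read to include early leavers?** No. Section 9.3.5 sets scheduled completion against premature discontinuation, and the Appendix A notes make the same contrast.

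**Appendix A footnote a.** It limits V7 to subjects whose second bronchoscopy was at V6. It is not counted as a conflict: 7.8 and the Appendix A notes apply the V6 (VE) procedures to premature endings, so V6 there can include an early VE. The completer condition in 9.3.6 has no such reading.

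**Count and weight.** Two sections carry a restriction (9.3.6 and 9.1.3), and six places tie the visit to the bronchoscopy without one. The six are not equal in weight. Sections 2.0 and 6.1 repeat one sentence, 6.2 is rationale, and the Appendix A note mainly fixes timing. Sections 9.1.15 and Appendix F are the direct operating instructions. Of the two restrictive sections, only 9.3.6 conditions the visit itself.

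**The case against.** The strongest reply is that 9.3.6 is incomplete rather than contradictory. Neither 9.3.6 nor 9.1.3 uses the word *only*, and neither says an early leaver shall have no visit. A site that holds the visit breaches nothing, while a site that omits it breaches 9.1.15 and Appendix F, so all the texts can be followed together by giving the visit. The one explicitly exclusive rule, Appendix A footnote a, turns on the bronchoscopy and not on completion.

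The group is also narrow. Subjects who withdraw consent have no further evaluations (7.8), and the rest must agree to an optional bronchoscopy. Other protection continues:

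- at least 2 h of monitoring and a 24 h emergency number (9.1.15);
- a telephone call within 24-48 h (Appendix F);
- adverse-event follow-up to 30 days after the treatment period (6.1) and monitoring until symptoms subside (10.2.1.2);
- the examination, vital signs, laboratory tests and adverse-event assessment at the early-termination visit itself.

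Much of this stands. The wording is not formally exclusive, the restriction in 9.1.3 covers only the examination, the group may be empty, and the remaining safeguards are real. The reply does not remove the point, because 9.3.6 is where a site looks to decide who has V7. Read in the ordinary way, a visit specified for scheduled completers is not owed to others. A careful investigator may reconcile the sections, but should not have to.

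**Conclusion.** The concern holds. For a randomized subject who discontinues after V3 and accepts the second bronchoscopy, 9.3.6 gives no V7, while 6.1, 9.1.15 and Appendix F require one. If 9.3.6 governs, the statement in 6.2 is untrue for that subject. If the other sections govern, 9.3.6 is wrong as written. It needs correcting on either reading.

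The consequence is limited to one in-person safety visit, with its physical examination, per affected subject. How many subjects that is cannot be derived: the protocol gives no rate of early-termination bronchoscopy, and the number may be zero. A secondary effect is that 10.2.1.1 ends adverse-event collection at V7, so these subjects have no end visit in that section, although the 30-day follow-up in 6.1 partly covers the gap. The primary CD8+ comparison, the error control and the sample size are unaffected. The conclusion assumes only that scheduled completion excludes premature discontinuation, as the protocol's own usage shows. The change should be made because it concerns participant safety and costs very little.

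**What to change.** - **Section 9.3.6:** replace the completer condition with *all randomized subjects who underwent the second bronchoscopy, at V6 or at early termination*, and time V7 within two weeks of that bronchoscopy.
- **Section 9.1.3:** delete *as planned*, so that the V7 examination follows the same rule.
- **Appendix A, footnote a (optional):** state that V6 includes an early VE.

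The cost is wording in two sections, one optional footnote clarification, and at most a few additional safety visits of a type the protocol already contains.

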9.3.7 Post Study Care

As Roflumilast is registered as DAXAS[®] and is marketed in several countries, Subjects may receive the medication after trial completion (V6). It is at the discretion of the respective Investigator to prescribe DAXAS[®] in countries where it is marketed. If the drug is not marketed in the respective country, no further treatment can be granted by the Sponsor.

The blinding of Subjects will be kept in any case until database freeze, unless unblinded according to Section 8.4.

9.4 Biological Sample Retention and Destruction

PPD's global central laboratory will supply the investigational site with the necessary equipment for storage, labelling and shipment of the samples.

Paraffin embedded biopsies, prepared as described in the Biopsy Laboratory Manual (Appendix G), can be stored and shipped at room temperature. Labelling and shipment are described in the Central Laboratory Manual.

The Investigator is responsible for the proper storage of biological samples (i.e. blood samples for standard safety laboratory analyses, blood samples for inflammatory biomarker analyses, sputum materials) at approximately -20°C or below (preferably -80°C) until sample shipment.

All biological samples have to be clearly and fully labelled according to the Central Laboratory Manual. Biological samples should be sorted by Subject and visit such that all the samples from a given Subject are readily accessible. A sample inventory list of all biological samples must be included in each sample shipment. Packing and shipment of the biological samples must be in accordance with the current guidelines.

Further details for storage, labelling and shipment of (a) biopsy paraffin blocks, (b) standard safety laboratory blood samples, (c) sputum cell count samples, (d) sputum biomarker samples, and (e) biomarker blood samples are described in the Central Laboratory Manual.

PPD will analyse the standard safety laboratory parameters immediately, while the serum and sputum supernatant samples for inflammatory biomarkers analyses will be stored at -80°C at PPD's global central laboratory. On Sponsor's request the stored samples will be sent on dry ice from PPD's global central laboratory to the Biomarker Laboratory (RBM, Austin, Texas) for analysis. PPD will be advised of the shipping details. Frequency of shipments will be discussed between the Sponsor and PPD by case situation.

Aliquots of sputum and tissue samples of the biopsy material will be collected and stored for up to three years after the end of the trial for future analyses of biomarkers of scientific interest.

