9.1.9 Procedures for Clinical Laboratory Samples

The central laboratory will provide the sites with appropriate material and a manual before the trial starts.

All samples will be collected in accordance with acceptable laboratory procedures. The maximum volume of blood at any single visit is approximately 18,5 mL, and the approximate total volume of blood for the study is 58 mL for all scheduled visits. Details of these procedures and required safety monitoring will be given in the laboratory manual.

Table 9.a Clinical Laboratory Tests

Hematology	Serum Chemistry	Urinalysis
Haemoglobin	Glucose	Glucose
Haematocrit,	Creatinine	Protein
Erythrocytes	Total bilirubin (in case of values above the normal range, direct and indirect bilirubin will be determined),	Blood
Thrombocytes,	Alkaline phosphatase (AP)	
Leukocytes	Aspartate aminotransferase (AST)	
Differential white blood cell (WBC) count	Alanine aminotransferase (ALT)	
	Gamma-Glutamyl transferase (GGT)	
	Creatine kinase (CK)	
	Sodium	
	Potassium	
	Total calcium	
	Cholesterol (total, low density lipoprotein, high density lipoprotein)	
	Triglyceride	
Other:		
Serum	Urine	
Female subjects of childbearing potential: human chorionic gonadotropin (hCG) for pregnancy	Female subjects of childbearing potential: hCG for pregnancy	

The central laboratory will perform laboratory tests for hematology, serum chemistries, and urinalysis.

The results of laboratory tests will be returned to the investigator, who is responsible for reviewing and filing these results.

The investigator will maintain a copy of the laboratory accreditation and the reference ranges for the laboratory used.

Analyses will be done by a central laboratory. Blood samples will be handled and stored according to the instructions provided by the central laboratory. All laboratory samples have to be clearly and fully labelled according to the Central Laboratory Manual. The laboratory reports received by fax from the central laboratory will be reviewed, signed and dated by the Investigator and attached to the CRF (including corrected reports).

Blood must be drawn under fasting conditions (8 hours).

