9.1.9.2 Clotting Time and Platelet Count

Blood sampling will be performed at visits V0, V1, and V5. Analyses of the clotting screen (PT, APTT, TT, INR and platelet count) will be done by the Central Safety Laboratory. Blood samples will be handled and stored according to the instructions provided by the Central Safety Laboratory. All laboratory samples have to be clearly and fully labelled according to the Central Laboratory Manual. The laboratory reports received by fax from the Central Safety Laboratory will be reviewed, signed and dated by the Investigator and attached to the CRF (including corrected reports).

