Appendix E Laboratory and Vital Sign Alert Values (Sponsor defined)

HEMATOLOGY

Hemoglobin: male < 11.5 g/dL female < 9.5 g/dL
Erythrocytes: male < 3.5 $10^6/\mu\text{L}$ or > 7 $10^6/\mu\text{L}$ female < 3.0 $10^6/\mu\text{L}$ or > 6.5 $10^6/\mu\text{L}$
White Blood Cell Count (WBC): < 2,800/mm³ or > 16,000/mm³
Eosinophils: > 20%
Platelet Count: < 75,000/mm³ or > 700,000/mm³

CHEMISTRY

SGOT (ASAT): > 3x ULNR
SGPT (ALAT): > 3x ULNR
Gamma-GT: > 3x ULNR
Alkaline Phosphatase (AP): > 3x ULNR
CK: > 3x ULNR;
Creatinine: > 2x ULNR
Total Bilirubin: > 2x ULNR
Potassium: > 6.0 mmol/L or < 3.0 mmol/L
Sodium: > 150 mmol/L or < 130 mmol/L
Glucose: > 2 x ULNR

VITAL SIGNS

BP systolic: > 170 mmHg or < 85 mmHg
BP diastolic: > 105 mmHg
Difference systolic BP at Vx (increase or decrease) compared to pre-treatment > 40 mmHg
Resting Heart Rate: > 120 bpm or < 50 bpm
Difference HR at Vx (increase or decrease) compared to pre-treatment > 30 bpm

ULNR = Upper Limit of Normal range

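### Protocol Section 9.4 tells sites to freeze standard safety blood without exception, although that panel includes cell counts that need unfrozen blood

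*Protocol*

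**What the plan says.** Section 9.4 gives one site storage rule for three kinds of material: "blood samples for standard safety laboratory analyses, blood samples for inflammatory biomarker analyses, sputum materials) at approximately -20°C or below", with -80°C preferred, until the samples are shipped. Safety blood is named first and no part of it is excepted. Later in the section, storage details for several sample types, safety blood among them as item (b), are referred onward in a list that ends "e) biomarker blood samples are described in the Central Laboratory Manual".

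Section 9.1.9 defines what safety blood is for: "The central laboratory will perform laboratory tests for hematology, serum chemistries, and urinalysis". The haematology column of Table 9.a has six entries: haemoglobin, haematocrit, erythrocytes, thrombocytes, leukocytes and "Differential white blood cell (WBC) count". On storage, Section 9.1.9 states no temperature: "Blood samples will be handled and stored according to the instructions provided by the central laboratory".

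Section 9.1.9.2 covers a separate draw at V0, V1 and V5: "Analyses of the clotting screen (PT, APTT, TT, INR and platelet count) will be done by the Central Safety Laboratory". It too leaves handling and storage to the laboratory's instructions.

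**The concern.** Freezing and thawing whole blood ruptures red cells, white cells and platelets. This is general laboratory knowledge and needs no outside source. A storage rule suited to separated serum or sputum supernatant is therefore wrong for a tube from which cells are to be counted. Section 9.1.9 itself treats haemolysis as making results unreliable and as grounds for a new investigation.

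What is at stake is safety data. The panel supports the eligibility check at V0 (exclusion criteria 9 and 10) and the end-of-treatment safety assessment at V6. It also feeds sponsor alert limits in Appendix E such as "Platelet Count: < 75,000/mm³ or > 700,000/mm³". A site following the sentence would face missing values, repeat draws or spurious abnormal results. If the Manual says not to freeze, a site that handled the blood correctly would be departing from the protocol as written.

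**Working it through.** The point involves no sample size, power or error rate, so there is no figure of the plan to reproduce. The check sets the relevant texts side by side.

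1. **Does the freezing rule name safety blood?** Yes. Section 9.4 lists the covered samples exhaustively and puts standard safety blood first. No tube type is excluded.

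2. **Does that blood include material for cell counts?** Yes. Of the six haematology entries in Table 9.a, haemoglobin is a concentration that can be measured in lysed blood. That leaves 6 - 1 = 5 entries needing intact cells: haematocrit, erythrocytes, thrombocytes, leukocytes and the differential count.

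3. **At which visits?** Appendix A schedules the standard laboratory at V0 and V6, and at V1 only to confirm or check V0 values (footnote d). There is none at V5. Under Section 9.3.5, the V6 assessments other than bronchoscopy also apply to subjects who stop prematurely after V3.

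4. **Which alert values depend on it?** Appendix E has five haematology alert values: haemoglobin, erythrocytes, WBC, eosinophils and platelets. Without haemoglobin, 5 - 1 = 4 could not be applied reliably.

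5. **Does other text override the rule?** Sections 9.1.9 and 9.1.9.2 leave storage to the laboratory, and Section 9.1.9 also requires samples to be collected, prepared and arranged for transport under its instructions. Section 9.4 fixes a temperature. Its own reference to the Manual is for further details, which add to the stated temperature and do not withdraw it. The texts therefore fit poorly together, and nothing says which prevails.

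6. **Is the sentence sound for its other contents?** Not entirely. It allows about -20°C for sputum materials, whereas Appendix H requires supernatant at -70°C to -80°C and has the cell-count material prepared as fixed slides, not frozen. This points to a sentence drafted for biomarker samples and worded too widely.

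**The case against.** The strongest reply is that handling is governed elsewhere. Sections 9.1.9 and 9.1.9.2 and the later part of Section 9.4 all point to the laboratory's instructions, the laboratory supplies the storage and shipping equipment, and experienced sites would be expected to follow the Manual. This stands as a limit on the likely harm. It does not repair the text: the complaint is not that a detail was left to another document, but that the protocol states an instruction that is wrong for these samples.

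A reader might also infer more than the documents support:

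- *That the platelet and clotting checks before each biopsy are compromised.* Appendix A lists these as a row separate from the standard laboratory, and Section 9.1.9.2 contains no freezing instruction. Section 9.4 names only standard safety blood, so its reach to these samples is an open question.
- *That no haematology alert value could be applied.* Haemoglobin may still be measurable.
- *That Section 9.4 contradicts itself by saying "PPD will analyse the standard safety laboratory parameters immediately".* That describes work at the central laboratory, in contrast to biomarker samples held there at -80°C. It hints at what the freezing was meant for, but it does not conflict with storage at the site.
- *That a run of false adverse events would follow.* Under Section 9.1.9, abnormal laboratory values at V0 are not adverse events, and haemolysed samples call for re-investigation. What remains is mainly V6, and V1 if repeated.
- *That the counts will in fact be lost.* No site is shown to follow the sentence.

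**Conclusion.** The point holds as an error of wording with a safety-data consequence. Followed literally, Section 9.4 would spoil five of the six haematology entries of Table 9.a at V0 and V6 (and at V1 if repeated), and four of the five haematology alert values in Appendix E could not be relied on. It is also not reconciled with Sections 9.1.9 and 9.1.9.2.

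The conclusion rests on two assumptions: that the listed counts are made on whole blood, which follows from the tests named, and that freezing destroys the cells. The actual extent of harm cannot be judged without the Central Laboratory Manual and is probably small. The primary CD8+ analysis, the key secondary CD68+ analysis and the sample size are untouched. The correction is worth making because it is cheap and protects safety results.

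**What to change.** In Section 9.4, limit the frozen-storage sentence to the samples it is meant for, namely biomarker serum and sputum supernatant. State that standard safety blood and clotting/platelet blood are stored and shipped only according to the Central Laboratory Manual; this also settles the unclear reach to the Section 9.1.9.2 samples. The protocol need not set out handling tube by tube. Then reconcile Section 9.4 with Sections 9.1.9 and 9.1.9.2, and with Appendix H on the supernatant temperature and the cell-count slides, and check that the Manual agrees.

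The cost is essentially a one-sentence protocol correction. No procedure, visit or analysis changes.
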